11.2 Criteria for Evaluation of Therapy Effectiveness

Progression-Free Survival

PFS is defined as the duration of time from start of treatment to time of progression or death, whichever occurs first.

Quality of life

Quality of life will be measured using the EORTC QLQ-BN20+2 and QLQ-C15-PAL questionnaires. These questionnaires will be given to the patient at the same time points as MMSE during the follow up visits.

12. ETHICAL AND REGULATORY CONSIDERATIONS

12.1 Protocol and Regulatory Compliance

The Investigator must conduct the study according to this protocol.

The study must be conducted by all Investigators in compliance with Good Clinical Practices (GCP) as defined as described in the U.S. FDA Code of Federal Regulations 21 CFR 312 (Investigational New Drug Application), 21 CFR 50 (Protection of Human Subjects), 21 CFR 54 (Financial Disclosure by Clinical Investigators), 21 CFR 56 (Institutional Review Boards) and ICH guidelines (Guideline to Good Clinical Practice).

The PI of this study is ultimately responsible for every aspect of the design, conduct and actions of all members of the research team. This includes the final analysis of the protocol.

All protocols include a Data Safety Monitoring Plan (DSMP) and procedures for its implementation commensurate with the risk and complexity of the study. The DSMP must include a structured adverse event determination, monitoring and reporting system, including standardized forms and procedures for referring and/or treating subjects experiencing adverse events. The plan must include data and safety-monitoring procedures for subjects enrolled who may be receiving a part of their protocol-required treatment at community sites.

The PI of this study will have primary responsibility for ensuring that the protocol is conducted as approved by the SRC and IRB. The PI will ensure that the monitoring plan is followed, that all data required for oversight of monitoring are accurately reported to a DSMP and/or to the Protocol Monitoring Committee (PMC) and IRB as required, that all adverse events are reported according to protocol guidelines, and that any adverse actions reflecting patient safety concerns are appropriately reported.

12.2 Document Audits and Monitoring

Data will be captured in Oncore, Moffitt's Clinical Trials Database. Regulatory documents and case report forms will be monitored internally according to Moffitt Cancer Center Monitoring Policies. Monitoring will be performed regularly to verify data is accurate, complete, and verifiable from source documents; and the conduct of the trial is in compliance with the currently approved protocol/amendments, Good Clinical Practice (GCP), and applicable regulatory requirements.

The PMC monitors its assigned ongoing research protocols monthly for: adverse event reporting, data and safety monitoring, and internal audit findings. The PMC upon review of any agenda item may approve the study for continuation, require revisions, suspend or close a protocol.

Investigators of studies which are designed to be reviewed by the PMC for data and safety monitoring, shall provide a statistical report of the study's progress and summary of adverse events and deviations based on the phase of the study and the associated risk of the study or more often if applicable. The external DSMP (if applicable) shall forward its report for high-risk studies designated for external review at least annually or more often if applicable.

12.3 Protocol Amendments

Any changes to this protocol will be initiated by the investigators or by the Regulatory Sponsor (Moffitt cancer Center) as a protocol amendment. The Investigator must submit the amendment to the IRB, with a revised Informed Consent Document if applicable. The Investigator must receive written approval from the IRB before the amendment may take effect.

12.4 Regulatory Binder

To be in compliance with GCPs, the Investigator must maintain accurate, complete, and organized documentation supporting the conduct of the study. This documentation includes, but is not limited to, the following: study personnel's qualifications and training, IRB approvals and communications, communications with the Regulatory Sponsor, Site Signature & Responsibility Log, laboratory accreditations and reference ranges, Form FDA 1572s, and Informed Consent Documents (copies of IRB approved versions, signed/dated originals, or copies for all enrolled patients).

12.5 Informed Consent

Prior to the performance of any protocol-specific procedures, informed consent must be obtained and documented by the use of a written Informed Consent Document approved by the Regulatory Sponsor and the IRB. The Informed Consent Document must be signed and dated by the patient or by the patient's legally authorized representative and by the person conducting the informed consent discussion. The Informed Consent Document must fulfill the requirements as contained in the U.S. Code of Federal Regulations (21 CFR 50.25), the ICH guidelines, and the Declaration of Helsinki. The Informed Consent Document must be written in a language understandable to the patient or to the representative.

A signed and dated copy of the Informed Consent Document must be given to the person signing the document. The original must be retained by the Investigator with the study documentation and be available for inspection by persons conducting an audit of the study.

Modifications to this template may be made by study site personnel to be in compliance with national, regional (e.g., state) or local laws and/or institutional requirements.

12.6 Institutional Review Boards

The protocol, Informed Consent Document, patient recruitment procedures (e.g., advertisements), information about payments and compensation available to patients, and any amendments must be approved by a properly constituted IRB in compliance with current regulations of the U.S. FDA, ICH guidelines, and any country-specific regulations.

12.7 Institutional Review Board/Independent Ethics Committee

Before study initiation, the investigator must have written and dated approval/favorable opinion from the IRB/IEC for the protocol, consent form, subject recruitment materials/process (eg, advertisements), and any other written information to be provided to subjects. The investigator or sponsor should also provide the IRB/IEC with a copy of the Investigator Brochure or product labeling, information to be provided to subjects and any updates. The investigator or sponsor should provide the IRB/IEC with reports, updates and other information (eg, expedited safety reports, amendments and administrative letters) according to regulatory requirements or institution procedures.

12.8 Curriculum Vitae and Medical Licenses

The Principal Investigator is responsible for ensuring that the study is being conducted by qualified personnel. Documentation of these qualifications must be maintained within the Regulatory Binder, and includes the following:

Curriculum Vitae (CV): CVs for the Principal Investigator and all Sub-investigators listed on the Form FDA 1572 must be signed and dated. These CVs must show affiliation with the institution conducting the study and be current within two years of the personnel initiating their participation in the study.

Medical Licenses: Medical licenses (physicians, physician assistants, nurses) listed on the Form FDA 1572 must be kept current, and copies must be maintained in the Regulatory binder during the entire period of the person's participation in the study.

12.9 Patient Confidentiality

The Investigator must ensure that the patient's confidentiality is maintained. Patient medical information obtained for the purposes of this study is confidential, and disclosure to third parties, other than those noted below, is prohibited. Patients should be identified only by their initials and protocol-assigned patient ID number. For those patients whose surgical specimen is processed and read by the central pathology laboratory, the patient's billing information will be requested by this laboratory and will not be shared with the sponsor or any of its affiliates or representatives.

Study personnel should follow the requirements of the Health Insurance Portability and Accountability Act (HIPAA).

All clinical information is confidential, but data generated for this study must be available for inspection on request to representatives of the U.S. FDA, other national or local regulatory or health authorities, Endo Pharmaceuticals representatives, and the associated IRB.

All records must be kept in a secured area.

12.10 Financial Disclosure

Documentation of each Investigator's proprietary or financial interest is required by the U.S. Code of Federal Regulations (21 CFR 54). A financial disclosure form provided by the Sponsor must be completed, signed, and dated by the Principal Investigator and each Sub-investigator listed on the Form FDA 1572. This form must be executed prior to the personnel's participation in the study. The original form will be retained by the Sponsor. Each Investigator must inform the Sponsor of any change in his/her financial interest in the Sponsor for up to one year after the end of the study.

13. DATA MANAGEMENT AND RECORD KEEPING

Data will be maintained by the Moffitt Cancer Center.

14. STATISTICAL CONSIDERATIONS

14.1 Study Design/Endpoints

This is a standard 3+3 design and will include 2 cohorts: 1) dose escalation cohort, and 2) dose expansion cohort.

Endpoints

• Primary endpoints

- To determine the maximum tolerated dose (MTD) of TPI 287 given concurrently with FSRT to treat brain metastases from advanced breast and non-small cell lung cancer
- To determine the safety and toxicity of TPI 287 given concurrently with FSRT to treat brain metastases from advanced breast and non-small cell lung cancer

• Secondary endpoints

- To determine the local control rate
- To determine the distant intra-cranial control rate
- To determine the short-term (≤ 30 days post-treatment) and long-term (> 30 days post treatment) adverse effects
- To determine the PFS
- To evaluate the effect of concurrent therapy with TPI 287 and FSRT on measures of quality of life

14.2 Sample Size/Accrual Rate

The number of patients needed for doe escalation phase will depend on the number of dose levels reached. The maximum size for the dose escalation phase will be 36 patients. In the dose expansion phase, a total of 10 patients (including patients treated at the MTD from dose escalation phase) will be enrolled to confirm the safety and to assess radiologic response.

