A Phase 1 Study of TPI 287 Concurrent with Fractionated Stereotactic Radiotherapy (FSRT) in Treatment of Brain Metastases from Advanced Breast and Non-Small Cell Lung (NSCL) Cancer

NCT02187822

Version 1.6

July 7, 2014

Title:A Phase 1 Study of TPI 287 Concurrent with Fractionated Stereotactic
Radiotherapy (FSRT) in Treatment of Brain Metastases from Advanced
Breast and Non-Small Cell Lung (NSCL) Cancer

Protocol Number: MCC 17816

- **IND Number:** 123010
- Sponsor:H. Lee Moffitt Cancer Center & Research Institute, Inc.
(Moffitt Cancer Center), Investigator Initiated Trial

Investigational Product: TPI 287

Principal Investigators:[name]
Department of Neuro-Oncology, Moffitt Cancer Center
[name]
[name]

Co-Investigators:

[name] [name] [name] [name] [name] [name] [name] [name], DO [name] [name], PhD

Statistician:

Original Protocol:

July 7th, 2014

PROTOCOL SYNOPSIS

TITLE	A Phase 1 Study of TPI 287 Concurrent with Fractionated Stereotactic Radiotherapy (FSRT) in Treatment of Brain Metastases from Advanced Breast and Non-Small Cell Lung (NSCL) Cancer	
STUDY PHASE	Ι	
PRIMARY	To evaluate the safety, tolerability, and to determine the maximum	
OBJECTIVES	tolerated dose (MTD) of TPI 287 given concurrently with fractionated stereotactic radiotherapy (FSRT) to treat brain metastases from advanced breast and non-small cell lung cancer.	
SECONDARY	To characterize the pharmacokinetics and anti-tumor effect of TPI 287	
OBJECTIVES	administered concurrently with FSRT in the treatment of patients with breast and NSCL cancers metastatic to the brain; and to evaluate the effect of treatment on measures of quality of life.	
HYPOTHESES	TPI 287, given concurrently with FSRT, will improve local control and decrease distant brain failure in patients with brain metastases from advanced breast and NSCL cancers.	
STUDY DESIGN	 Dose escalation phase: The MTD for TPI 287 given concurrently with FSRT will be determined using the standard 3+3 study design. Dose expansion phase: Patients will be treated with TPI 287 at MTD given concurrently with FSRT to further assess toxicity and tumor response. 	
PRIMARY	Primary endpoints:	

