interrupted dose at a slower infusion rate (half of the rate at which hypersensitivity reaction occurred) pending all signs and symptoms of hypersensitivity have resolved. If a \geq Grade 3 hypersensitivity reaction is observed, the TPI 287 infusion will be stopped and appropriate supportive care administered until the symptoms resolve. The subject will be discontinued from the trial.

Dose Definition

Dose Escalation Phase:

The starting dose (i.e., dose level 1) will be 14 mg/m^2 /dose. Provided that MTD has not been reached, the TPI 287 dose will be increased as follows:

Dose Escalation Schedule		
Dose Level	Dose	
	TPI 287 IV	Radiotherapy
Level -2	5 mg/m ² /dose	5 Gy daily fraction
Level -1	7 mg/m ² /dose	5 Gy daily fraction
Level 1	14 mg/m ² /dose	5 Gy daily fraction
Level 2	28 mg/m ² /dose	5 Gy daily fraction
Level 3	56 mg/m ² /dose	5 Gy daily fraction
Level 4	85 mg/m ² /dose	5 Gy daily fraction
Level 5	113 mg/m ² /dose	5 Gy daily fraction
Level 6	$127.5 \text{ mg/m}^2/\text{dose}$	5 Gy daily fraction

Table 1. Dose Escalation Schedule

If dose level 1 is found to cause unacceptable toxicity, the dose will be de-escalated to levels -1 or -2.

Dose Expansion Phase:

The TPI 287 dose used in the dose expansion cohort will be MTD determined from the dose escalation phase. TPI 287 will be administered intravenously prior to treatment of brain metastasis with FSRT on day 1 and will be given for 2 more weekly doses. The prescription dose of FSRT will be 25 Gy in 5 daily fractions as described in section 5.2.

Definition of Maximum Tolerated Dose:

The maximum tolerated dose (MTD) is the highest dose of TPI 287 that does not cause unacceptable toxicity in more than one of six patients at that dose level. The MTD is defined as one dose level below the highest toxic dose (i.e., the DLT dose).

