5.4 Definition of Dose-Limiting Toxicity

Toxicities will be graded in severity according to the guidelines outlined in the NCI-CTCAE version 4.0. Dose limiting CNS and non-CNS (hematologic and non-hematologic) toxicities will be defined differently and will be based on events that occur during the study period. In order to be declared as dose-limiting toxicity, an adverse event must be related (definite, probable, or possible) to study treatment.

A dose-limiting toxicity (DLT) will be defined as any one of the following adverse events occurring within 8 weeks from last dose of radiation therapy:

CNS toxicities:

Acute CNS toxicities (occurring \leq 30 days after completing FSRT treatment):

• Any grade 3 or higher central nervous adverse events including but not limited to headache, dizziness, vertigo, new onset seizures, cerebral edema, cerebral hemorrhage, and new onset neurologic deficit.

Delayed onset CNS toxicities (occurring >30 days after completing FSRT treatment):

 Any grade 3 or 4 adverse event arising within the irradiated volume including but not limited to radiation necrosis or focal neurological deficits.

Non-CNS toxicities:

Non-hematologic toxicities:

- Any grade 3 or higher non-hematologic adverse event with the exception of alopecia, fatigue, and anorexia.
- Grade 3 or higher nausea and/or vomiting that persists ≥ 48 hours despite optimal medical management.

Hematologic toxicities:

- Grade 4 neutropenia lasting for \geq 7 days in duration
- Grade \geq 3 febrile neutropenia with/without infection

• Grade 4 thrombocytopenia

Dose escalation will be determined based on the occurrence of DLTs. For the purposes of determining whether to advance the dose levels, DLTs will be counted by patient. In the event of the development of any grade 3 or 4 toxicity felt to be at least possibly related to study drug, TPI 287 will be held until resolution to grade 1 or baseline assuming that occurs within 15 day window.

Dose escalation will follow the standard 3+3 design. The enrollment to next higher dose level will be delayed for 8 weeks after the completion of FSRT by the last patient enrolled at the dose level. This period of 8 weeks will allow monitoring potential delayed toxicities. Management and dose modifications associated with the above adverse events are outlined in Section 6. Dose escalation will proceed according to the following scheme. Dose-limiting toxicity (DLT) is defined above.

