Number of Patients with DLT at a Given Dose Level	Escalation Decision Rule
0 out of 3	Enter 3 patients at the next dose level.
≥2	Dose escalation will be stopped. This dose level will be declared the maximally administered dose (highest dose administered). Three (3) additional patients will be entered at the next lowest dose level if only 3 patients were treated previously at that dose.
1 out of 3 or ≥ 2 grade 2 CNS toxicities	 Enter at least 3 more patients at this dose level. If 0 of these 3 patients experience DLT, proceed to the next dose level. If 1 or more of this group suffer DLT, then dose escalation is stopped, and this dose is declared the maximally administered dose. Three (3) additional patients will be entered at the next lowest dose level if only 3 patients were treated previously at that dose.
≤1 out of 6 at highest dose level below the maximally administered dose	This is the dose to be used in the expanded cohort and will be considered recommended phase 2 dose. At least 6 patients must be entered at this dose.

Table 2. Dose Escalation Rules

If dose level 1 is found to cause unacceptable toxicity, the dose will be de-escalated to level -1 (7 mg/m^2). Three patients will be enrolled at dose level -1. If no DLT is observed, three additional patients will be enrolled at dose level -1 such that safety is established in at least 6 patients prior to entering dose expansion phase.

Any delayed CNS-toxicity arising within the radiation field but seen beyond the window for DLT registration (> 8weeks following completion of FSRT) will be recorded. Furthermore, occurrence of any delayed-onset treatment related grade 3 or higher central nervous toxicity at any time (during and after DLT period of 8 weeks) will lead to holding dose-escalation and adding 3 patients to the dose level at which toxicity has occurred. Occurrence of additional delayed-onset treatment related grade 3 or higher CNS- toxicity will be reviewed with Protocol Monitoring Committee and IRB to determine whether discontinuation or modification of trial is subsequently warranted.

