5.9 Stopping Rules

The expected rate of neurologic death with FSRT alone is 13-14%. ^{24,25} The reported rate for symptomatic radiation necrosis is 7.7%. ²⁴ A higher rate of neurologic death (> 14%) or symptomatic brain necrosis (> 10%) in this study would imply that the combination of FSRT and TPI 287 is excessively toxic and not suitable for further clinical development. In addition grade \geq 3 delayed-onset toxicity in this study would imply that the combination of FSRT and TPI 287 is excessively toxic and not suitable for further clinical development. In addition, the results will be discussed with Cortice Bioscience, Protocol Monitoring Committee and IRB and study will be closed. In addition, occurrence of other delayed-onset treatment related grade 3 or higher CNS- toxicity will be monitored closely and reviewed with Protocol Monitoring Committee and IRB to determine whether discontinuation of trial is subsequently warranted.

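### The expansion meant to confirm safety counts at least 6 of its 10 patients from a cohort selected for at most 1 DLT, so the pooled DLT rate is biased low, and no general rule says how DLTs in the new patients bear on the RP2D

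*Combined protocol and SAP*

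**What the plan says.** Section 14.2 sets the expansion as follows: "a total of 10 patients (including patients treated at the MTD from dose escalation phase) will be enrolled to confirm the safety". The sentence goes on to give radiologic response as a second purpose. The synopsis describes the phase in similar terms: "Patients will be treated with TPI 287 at MTD given concurrently with FSRT to further assess toxicity and tumor response".

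The row of Table 2 (section 5.4) that leads to expansion is headed "≤1 out of 6 at highest dose level below the maximally administered dose". For that dose it states "This is the dose to be used in the expanded cohort and will be considered recommended phase 2 dose" and "At least 6 patients must be entered at this dose". Section 5.3 says the MTD "is the highest dose of TPI 287 that does not cause unacceptable toxicity in more than one of six patients at that dose level".

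On the use of DLTs, section 5.4 says "Dose escalation will be determined based on the occurrence of DLTs". The DLT window is 8 weeks from the last radiotherapy dose. Section 14.3 provides descriptive summaries over all patients, with no interval, no split by cohort and no allowance for selection.

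Three provisions also reach expansion patients:
- Section 5.9 says "A higher rate of neurologic death (> 14%) or symptomatic brain necrosis (> 10%) in this study would imply that the combination" is too toxic to develop further. It says the same of grade 3 or higher delayed-onset toxicity, and it provides for closing the study.
- Section 5.4 sends repeated delayed grade 3 or higher CNS toxicity to the Protocol Monitoring Committee (PMC) and IRB, who may stop or change the trial.
- Section 12.2 has the PMC monitor monthly, with power to ask for changes, suspend or close.

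**The concern.** A set of patients that is in the analysis because few of them had DLTs cannot give an unbiased DLT rate. Adding a few new patients dilutes the bias but does not remove it. The bias grows with the true rate, so it flatters most the doses that the expansion ought to expose.

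The MTD, the RP2D and safety are the primary endpoints. If the 10 are summarized as one group, the toxicity at the dose carried to phase 2 will tend to look lower than it is. If the new patients do badly, the plan has no DLT-based step for going back to the RP2D, which Table 2 names before any of them is treated.

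**Working it through.** **Plan's own figures.** The escalation maximum of 36 reproduces as 6 upward dose levels (Table 1) × 6 patients = 36. The 10 cannot be reproduced: section 14.2 gives no assumed rate, precision target or threshold.

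**Inputs.** Total 10 (14.2). At least 6 at the dose, with at most 1 DLT in 6 (Table 2). New patients: at most 10 − 6 = 4. The true DLT rate p is not in the documents. I assume 10%, 16.7%, 30% and 40%; one in six is the only benchmark the protocol offers (5.3).

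**Step 1, chance that a dose passes.** P(pass) = (1−p)^6 + 6p(1−p)^5. At p = 0.30: 0.1176 + 0.3025 = 0.420.

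**Step 2, expected DLTs in the selected six.** E[X | X ≤ 1] = 6p(1−p)^5 / P(pass), which simplifies to 6p/(1+5p). At p = 0.30: 1.8/2.5 = 0.72 DLTs, against 1.8 without selection.

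**Step 3, expected pooled rate.** (6p/(1+5p) + 4p)/10. At p = 0.30: (0.72 + 1.20)/10 = 0.192. At p = 0.40: (0.80 + 1.60)/10 = 0.240.

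**Step 4, what the new patients may show.** P(at least 2 of 4) = 1 − (1−p)^4 − 4p(1−p)^3. At p = 0.40: 1 − 0.1296 − 0.3456 = 0.525.

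| True rate (assumed) | P(pass) | Expected pooled rate | Bias (points) | P(≥2 DLTs in 4 new) |
|---|---|---|---|---|
| 10% | 0.886 | 8.0% | −2.0 | 0.052 |
| 16.7% | 0.737 | 12.1% | −4.5 | 0.132 |
| 30% | 0.420 | 19.2% | −10.8 | 0.348 |
| 40% | 0.233 | 24.0% | −16.0 | 0.525 |

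The last column applies to doses that have already passed. The joint chance of passing and then seeing at least 2 DLTs in 4 is 0.420 × 0.348 = 0.146 at 30%, and 0.233 × 0.525 = 0.122 at 40%.

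**Step 5, precision.** Two-sided 95% Clopper-Pearson limits: 0/4 gives 0 to 60.2%, 1/4 gives 0.6% to 80.6%, 0/10 gives 0 to 30.8% and 1/10 gives 0.3% to 44.5%. The 10-patient intervals do not allow for the selection.

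**Step 6, which DLTs have a written consequence.** Setting the DLT list in 5.4 beside 5.9 and the delayed-toxicity clause, delayed CNS events are covered, as are neurologic deaths and symptomatic necrosis above their limits. Non-fatal acute grade 3 or higher CNS events, prolonged grade 4 neutropenia, febrile neutropenia, grade 4 thrombocytopenia and most other non-CNS DLTs are not. A result of 1/6 followed by 3/4, or 4/10 pooled, has no defined reading: the MTD definition is framed on six patients and is not extended to 10.

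**The case against.** The strongest reply has five parts.

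- **Expansion results can have consequences.** A reader might infer that nothing seen in the expansion can touch the RP2D. The documents do not support that. Section 5.9 is study-wide and can close the trial, the delayed CNS review in 5.4 can change it, and the PMC can require changes. Some of the events covered are themselves DLTs. This stands, and it limits the gap to DLTs outside those provisions and to the absence of a stated criterion.
- **Something is confirmed.** A reader might infer that the expansion confirms nothing. That also goes too far. Up to 4 new patients give unbiased, if very imprecise, DLT data. Response and late toxicity, followed to 18 months, are not directly selected on.
- **The bias is small at the protocol's benchmark.** At one in six it is 4.5 points, or 0.45 of a patient in 10, against a standard error of √(1/6 × 5/6 / 10) = 11.8 points. True, but confirmation matters most when the rate is higher, and there the bias reaches 11 to 16 points.
- **No pooled DLT rate is named as an endpoint.** Correct. Section 7.3 lists adverse events by patient, so the cohorts could be separated. But 14.2 assigns the 10 to confirming safety and 14.3 asks only for overall summaries, so the pooled figure is the natural output.
- **Table 2 has a row for 2 or more DLTs, with no denominator.** It could be read across to the expansion, but the table governs escalation, and that row's first consequence is to stop an escalation already over.

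Counting escalation patients in an expansion is common. The objection here is to treating the total as confirmation without a split, an interval or a decision rule.

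**Conclusion.** The point holds in this limited form. At least 6 of the 10 were selected for few DLTs, at most 4 are new, and the expected pooled DLT rate is below the true rate at every value checked: by 2.0 points at 10%, 4.5 at one in six, 10.8 at 30% and 16.0 at 40%. Among doses that passed the rule, at least 2 of 4 new patients would have a DLT in 35% of cases at a true 30% and 53% at a true 40%. Outside 5.9, the delayed CNS review and the PMC's general powers, the documents do not say what that would mean for the RP2D.

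The sizes rest on assumed true rates, independent patients, and exactly 6 carried over. They ignore the route by which grade 2 CNS toxicities enlarge a cohort. The number of new patients is a ceiling: if the delayed-toxicity clause added 3 to a level that already had 6, only 10 − 9 = 1 would be new. The bias concerns DLTs within the 8-week window.

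**What to change.** - **Section 14.3.** Report DLT and toxicity rates for newly enrolled expansion patients separately from those carried over from escalation, each with an exact binomial interval. If a pooled DLT rate is also given, label it as conditional on the dose having passed the selection rule.
- **Table 2.** Call the RP2D provisional until the expansion cohort's 8-week DLT window has closed and the PMC has reviewed the DLT count at that dose against a criterion the sponsor fixes in advance. The sponsor should also state how that review relates to 5.9 and to the delayed CNS clause in 5.4. No boundary or dose is proposed here.

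The cost is wording in two places and one defined review by a committee that already meets monthly, with no new patients. The downside is a wider and less favourable reported rate (a separate 0/4 still has an upper limit of 60.2%) and a small chance that the RP2D is reconsidered.
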